3.1.1 Administrative structure of the trial

The trial is sponsored by Boehringer Ingelheim (BI) Pharma GmbH & Co. KG, Germany.

BI has appointed a Trial Clinical Monitor, responsible for coordinating all required activities, in order to

- manage the trial in accordance with applicable regulations and internal SOPs,
- direct the clinical trial team in the preparation, conduct, and reporting of the trial,
- ensure appropriate training and information of local clinical monitors (CML), Clinical Research Associates (CRAs), and participating trial sites.

The trial medication will be provided by the Clinical Trial Supplies Unit (CTSU), BI Pharma GmbH & Co. KG, Biberach, Germany.

Trial Protocol

c15848749-03 Page 33 of 84

Proprietary confidential information © 2018 Boehringer Ingelheim International GmbH or one or more of its affiliated companies

The trial will be conducted at

under the supervision of the Principal

Investigator.

Safety laboratory tests will be performed by the local laboratory of the trial site

The analyses of BI 1265162 concentrations in plasma and urine will be performed at the Department of Drug Metabolism and Pharmacokinetics, BI Pharma GmbH & Co. KG, Biberach, Germany.

The digitally recorded 12-lead ECGs will be sent to a specialised contract research organisation () for evaluation.

On-site monitoring will be performed by BI or a contract research organisation appointed by BI.

Data management and statistical evaluation will be done by BI or a contract research organisation appointed by BI according to BI SOPs.

Tasks and functions assigned in order to organise, manage, and evaluate the trial are defined according to BI SOPs. A list of responsible persons and relevant local information can be found in the ISF.

3.2 DISCUSSION OF TRIAL DESIGN, INCLUDING THE CHOICE OF **CONTROL GROUP**

For multiple-rising dose trials, the design described in Section 3.1 is viewed favourable under the provision not to expose the subjects involved to undue risks since the main study objective is to investigate safety and tolerability of BI 1265162.

With the rising dose design, double-blind conditions regarding the subject's treatment (active or placebo) are maintained within each dose group. However, the current dose level will be known to subjects and investigators. The disadvantage of this trial design is a possible observer bias with regard to the dose-depending effects as well as time effects, but it has the virtue of minimizing subject risk by sequentially studying ascending doses. As time-effects are expected to be small relative to the differences between the doses in the broad range investigated, unbiased comparisons between treatments can still be expected.

It is standard in trials involving healthy volunteers to include a placebo group as control for the evaluation of safety and tolerability. Each dose group consists of 10 subjects with 8 on active treatment, and 2 on placebo. The placebo control group includes all subjects of all dose groups treated with placebo. 8 subjects per active treatment group are in general considered as sufficient for the exploratory evaluation of pharmacokinetics.

Page 34 of 84

Proprietary confidential information © 2018 Boehringer Ingelheim International GmbH or one or more of its affiliated companies

After the first dose (single dose segment), a sufficient wash-out period will be included before the second dose (first dose of the multiple dose segment) is administered. This will allow for appropriate calculation of the pharmacokinetic parameters after a single dose administration and for comparison with pharmacokinetic parameters at steady state.

3.3 SELECTION OF TRIAL POPULATION

It is planned that 50 healthy males will enter the study. The actual number of subjects entered may exceed the total of 50 if additional intermediate doses will be tested (see Section 3.1). Subjects will be recruited from the volunteers' pool of the trial site.

Only male subjects will be included into the study because hitherto no data on reproductive toxicology are available.

A log of all subjects enrolled into the trial (i.e. having given informed consent) will be maintained in the ISF at the investigational site irrespective of whether they have been treated with investigational drug or not.

3.3.1 Main diagnosis for study entry

The study will be performed in healthy subjects.

3.3.2 Inclusion criteria

Subjects will only be included into the trial, if they meet the following criteria:

Subjects will only be included into the trial, if they meet the following criteria:

- 1. Healthy male subjects according to the assessment of the investigator, based on a complete medical history including a physical examination, vital signs (BP, PR), 12-lead ECG, and clinical laboratory tests
- 2. Age of 18 to 45 years (incl.)
- 3. BMI of 18.5 to 29.9 kg/m^2 (incl.)
- 4. FEV₁ and FVC of equal or greater than 80% of predicted normal, at screening and prior to randomisation
- 5. Signed and dated written informed consent prior to admission to the study in accordance with GCP and local legislation

3.3.3 Exclusion criteria

Subjects will not be allowed to participate if any of the following general criteria apply:

- 1. Any finding in the medical examination (including BP, PR or ECG) is deviating from normal and judged as clinically relevant by the investigator
- 2. Repeated measurement of systolic blood pressure outside the range of 90 to 140 mmHg, diastolic blood pressure outside the range of 50 to 90 mmHg, or pulse rate outside the range of 50 to 90 bpm

- 3. Any laboratory value outside the reference range that the investigator considers to be of clinical relevance
- 4. Any evidence of a concomitant disease judged as clinically relevant by the investigator
- 5. Gastrointestinal, hepatic, renal, respiratory, cardiovascular, metabolic, immunological or hormonal disorders
- 6. Cholecystectomy and/or surgery of the gastrointestinal tract that could interfere with the pharmacokinetics of the trial medication (except appendectomy and simple hernia repair)
- 7. Diseases of the central nervous system (including but not limited to any kind of seizures or stroke), and other relevant neurological or psychiatric disorders
- 8. History of relevant orthostatic hypotension, fainting spells, or blackouts
- 9. Chronic or relevant acute infections
- 10. History of relevant allergy or hypersensitivity (including allergy to the trial medication or its excipients)
- 11. Use of drugs within 30 days prior to administration of trial medication if that might reasonably influence the results of the trial (incl. QT/QTc interval prolongation)
- 12. Participation in another trial where an investigational drug has been administered within 60 days prior to planned administration of trial medication, or current participation in another trial involving administration of investigational drug
- 13. Smoker (more than 10 cigarettes or 3 cigars or 3 pipes per day)
- 14. Inability to refrain from smoking on specified trial days
- 15. Alcohol abuse (consumption of more 30 g per day for males)
- 16. Drug abuse or positive drug screening
- 17. Blood donation of more than 100 mL within 30 days prior to administration of trial medication or intended donation during the trial
- 18. Intention to perform excessive physical activities within one week prior to administration of trial medication or during the trial
- 19. Inability to comply with dietary regimen of trial site
- 20. A marked baseline prolongation of QT/QTc interval (such as QTc intervals that are repeatedly greater than 450 ms in males) or any other relevant ECG finding at screening
- 21. A history of additional risk factors for Torsades de Pointes (such as heart failure, hypokalemia, or family history of Long QT Syndrome)
- 22. A history of chronic kidney disease (EGFR <59 mls/min including corrections as per ethnicity)
- 23. Subject is assessed as unsuitable for inclusion by the investigator, for instance, because considered not able to understand and comply with study requirements, or has a condition that would not allow safe participation in the study
- 24. The subject has a diagnosis history of pulmonary hyperreactivity
- 25. Cannot use Respirat® appropriately

Page 36 of 84

Proprietary confidential information © 2018 Boehringer Ingelheim International GmbH or one or more of its affiliated companies

26. Male subjects with WOCBP partner who are unwilling to use male contraception (condom or sexual abstinence) from the first administration of trial medication until 14 days after last administration of trial medication (BI 1265162 or placebo)

For study restrictions, refer to Section 4.2.2.

3.3.4 Removal of subjects from therapy or assessments

3.3.4.1 Removal of individual subjects

An individual subject is to be removed from the trial if:

- The subject withdraws consent for trial treatment or trial participation, without the need to justify the decision
- The subject needs to take concomitant drugs that interfere with the investigational product or other trial medication
- The subject is no longer able to participate for other medical reasons (such as surgery, adverse events (AEs), or diseases)
- The subject shows an elevation of AST and/or ALT ≥3-fold ULN combined with an elevation of total bilirubin ≥2-fold ULN (measured in the same blood sample) and/or needs to be followed up according to the 'DILI checklist' provided in the ISF.

In addition to these criteria, the physician may discontinue subjects at any time based on his or her clinical judgment.

A subject can also be removed from the trial if eligibility criteria are being violated or if the subject fails to comply with the protocol (for instance, by non-adherence to dietary rules, or non-attendance at study assessments).

If a subject is removed from or withdraws from the trial prior to first administration of trial medication, the data of this subject will not be entered in the case report form (CRF) or trial database and will not be reported in the clinical trial report (CTR). If a subject is removed from or withdraws from the trial after first administration of trial medication, this will be documented and the reason for discontinuation must be recorded in the CRF. In this case, the data will be included in the CRF/trial database and will be reported in the CTR. At the time of discontinuation a complete end of trial examination will be performed if possible and the information will be recorded in the CRFs. If the discontinuation occurs before the end of the REP (see Section 5.2.2.2), the discontinued subject should if possible be questioned for AEs and concomitant therapies at or after the end of the REP in order to ascertain collection of AEs and concomitant therapies throughout the REP, if not contrary to any consent withdrawal of the subject. These discontinuations will be discussed in the CTR.

3.3.4.2 Discontinuation of the trial by the sponsor

Boehringer Ingelheim reserves the right to discontinue the trial overall or at a particular trial site at any time for any of the following reasons:

Proprietary confidential information © 2018 Boehringer Ingelheim International GmbH or one or more of its affiliated companies

- New toxicological findings or serious adverse events invalidate the earlier positive benefit-risk-assessment. Dose escalation will be terminated if more than 50% of the subjects at one dose level show drug-related and clinically relevant adverse events of moderate or severe intensity, or if at least one drug-related serious adverse event is reported.
- The expected enrolment goals overall or at a particular trial site are not met
- Violation of GCP, or the CTP or the contract with BI by a trial site or investigator, disturbing the appropriate conduct of the trial
- The sponsor decides to discontinue the further development of the investigational product.
- Dose escalation will be stopped as soon as at least 2 subjects at one dose level on active drug showed relevant individual QT prolongation, i.e. a QTc increase of greater 60 ms from baseline in connection with absolute QT or QTc greater than 500 ms, which has been confirmed by a repeat ECG recording.
- Dose escalation will be stopped as soon as at least 2 subjects at one dose level on active drug showed serum potassium levels > 5.5 mmol/L in non-hemolyzed blood

The investigator / the trial site will be reimbursed for reasonable expenses incurred in case of trial termination (except in case of the third reason).

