3. DESCRIPTION OF DESIGN AND TRIAL POPULATION

3.1 OVERALL TRIAL DESIGN AND PLAN

This multiple-rising dose trial is designed as double-blind, randomised, and placebocontrolled within parallel dose groups.

A total of 50 healthy male subjects is planned to participate in the trial, according to 5 sequential groups comprising 10 subjects per group. However, additional subjects may be entered to allow testing of additional doses on the basis of experience gained during the trial conduct, provided the planned and approved highest dose will not be exceeded. Thus, the actual number of subjects entered may exceed 50, but will not exceed 70 subjects entered. Such changes may be implemented via non-substantial CTP Amendments.

Within each dose group, 8 subjects will receive the active drug and 2 will receive placebo. Only one dose is tested within each dose group. Each dose group will consist of 2 cohorts (5 subjects each, 4 on active drug and 1 on placebo) which will be treated subsequently for safety reasons. The time interval between these cohorts will be at least 70 hours from first subject dosed.

The dose groups to be evaluated are outlined in Table 3.1: 1 below.

Table 3.1: 1 Dose groups

Dose Group	1	2	3	4	5	
Dose (µg) bid	10	30	100	300	600	
Number of subjects	10	10	10	10	10	
Subjects receiving placebo	2	2	2	2	2	
Subjects receiving active drug	8	8	8	8	8	

The dose groups will be investigated consecutively in ascending order of doses, maintaining a time interval of at least 5 days between the last drug administration in the previous dose group and the first drug administration of the subsequent dose group. The decision to proceed to the next dose group will be based upon the safety and tolerability of the preceding dose groups. The next dose will only be given if, in the opinion of the investigator, no safety concerns arose in the preceding dose group (i.e. no dose-limiting events occurred) and if none of the pre-specified trial-specific stopping criteria were met (refer to Section 3.3.4.2).

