A documented Safety Review must take place prior to each dose escalation. Furthermore, an unscheduled safety review meeting can be requested anytime for any reasonable cause by the Principal Investigator (or an authorised deputy) or the sponsor of the study, e.g. because of any unforeseen adverse events, etc. Dose escalation will only be permitted if no safety concerns exist in the opinion of the Principal Investigator (or an authorised deputy) and the trial clinical monitor (or an authorised deputy).

Although no formal Safety Review meeting will take place within a given dose group, safety will be continuously monitored during this trial, and an individual will only be dosed in the

Page 32 of 84

Proprietary confidential information © 2018 Boehringer Ingelheim International GmbH or one or more of its affiliated companies

absence of any safety concern (i.e. no dose-limiting events occurred) and if none of the prespecified trial-specific stopping criteria have been met (refer to Section 3.3.4.2).

The minimum data set for review consists of the following data:

- AEs in the current and preceding dose groups (including clinically relevant findings from ancillary safety testing listed below) (Note: AEs may be ongoing at the time of Safety Reviews and AE information may be subject to change prior to Database Lock)
- Results from 12-lead EGG in the current and preceding dose groups.
- Vital signs in the current and preceding dose groups
- Spirometry data
- Clinical laboratory tests in the current and preceding dose groups
- Check of criteria for stopping subject treatment as per Section 3.3.4.1

The decision to escalate the dose will be made jointly by the Principal Investigator (or an authorised deputy) and the trial clinical monitor (or an authorised deputy) after in-depth analysis of all available safety data, especially SAEs (if occurred), AEs and out-of-range laboratory results (if considered clinically significant). Safety Reviews can be conducted face-to-face or by video/telephone conference. The trial clinical monitor is responsible for organization and minutes of the reviews. Minutes will be signed off by the Principal Investigator (or an authorised deputy) and filed in the ISF and TMF.

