4.1.4 Drug assignment and administration of doses for each subject

The treatments to be evaluated are outlined in Table 4.1.4: 1 below. The number of actuations for placebo corresponds to the number of actuations of the respective dose level.

Table 4.1.4: 1 BI 1265162 and placebo treatments, inhalative administration

Dose	Substance	Pharmaceutical form	Dose per actuation (BI 1265162, administered dose)	Number of device actuations per single dose	Total daily dose (Day 1 and 8)	Total daily dose (Day 2-7)
1	BI 1265162	inhalation solution, RESPIMAT	10 μg	1	10 μg	20 μg
2	BI 1265162	inhalation solution, RESPIMAT	10 μg	3	30 μg	60 μg
3	BI 1265162	inhalation solution, RESPIMAT	100 μg	1	100 μg	200 μg
4	BI 1265162	inhalation solution, RESPIMAT	100 μg	3	300 μg	600 μg
5	BI 1265162	inhalation solution, RESPIMAT	100 μg	6	600 µg	1200 μg
1-5	Placebo*	inhalation solution, RESPIMAT		identical to active treatment for that dose level		

^{*} Subjects receiving placebo are equally distributed across dose groups

On Day 1 and 8 subjects will receive a single (qd) dose in the morning only. On all other trial days (2-7) BI 1265162 will administered bid.

Trial Protocol

Page 40 of 84

Proprietary confidential information © 2018 Boehringer Ingelheim International GmbH or one or more of its affiliated companies

Each newly assembled RESPIMAT Inhaler has to be primed by an unblinded (not involved in the conduct of the trial) qualified medical/pharmaceutical staff at the trial site under the responsibility of the investigator. To avoid contamination, except those devices used for training, priming should NOT take place in the same room where the subject is inhaling trial medication or the trial will be performed or samples will be processed. The inhaler should be primed under e.g. hood/outside by actuating it until an aerosol is visible plus three additional actuations. All priming actuations should be directed to the ground. For detailed priming instructions please refer to the RESPIMAT Inhaler handling instructions in Appendix 10.1.

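### Read literally, the AE rule for ending dose escalation counts placebo subjects, so 5 of 8 actively treated subjects with qualifying events and no placebo event would not meet it; the effect is narrow and the fix is one phrase

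*Protocol*

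**What the plan says.** Protocol section 3.3.4.2 lists the conditions that end escalation.

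- **Adverse events:** "Dose escalation will be terminated if more than 50% of the subjects at one dose level show drug-related and clinically relevant adverse events"; only events graded moderate or severe qualify. The same sentence adds a separate trigger: "or if at least one drug-related serious adverse event is reported".
- **Potassium:** "Dose escalation will be stopped as soon as at least 2 subjects at one dose level on active drug showed serum potassium levels" above 5.5 mmol/L in non-haemolysed blood.
- **QT:** also at least 2 subjects at one dose level, again restricted to those on active drug.

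Placebo subjects belong to a dose level. Section 3.1 says "Within each dose group, 8 subjects will receive the active drug and 2 will receive placebo", and section 4.1.4 says "The number of actuations for placebo corresponds to the number of actuations of the respective dose level". Each group is dosed as two cohorts of 4 active and 1 placebo.

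The criteria apply at two levels. Under section 3.1 the next dose level requires, among other things, "if none of the pre-specified trial-specific stopping criteria were met". Within a group there is no formal Safety Review, but "safety will be continuously monitored during this trial, and an individual will only be dosed in the" absence of a safety concern and "if none of the prespecified trial-specific stopping criteria have been met".

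Neither the protocol nor the SAP restricts the AE denominator to active subjects or turns the percentage into a count. The SAP does not deal with the escalation rules.

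**The concern.** An escalation threshold should track how the drug is tolerated. Two placebo subjects in the denominator dilute it when events occur only on active drug. The rule then behaves oddly: five active subjects with qualifying events and a clean placebo pair does not stop escalation, whereas the same five plus one placebo event judged drug-related does. The first pattern is the stronger evidence of a drug effect.

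The phrase about drug-relatedness does not cure this. It qualifies the event, not the people counted. Relatedness is judged by site staff who are blinded to active or placebo (sections 5.2.2.1 and 4.1.5.1), so a placebo event can be called drug-related.

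At stake is one prespecified stop before a dose step of two- to just over threefold (10, 30, 100, 300, 600 µg).

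**Working it through.** **Inputs.** Full group: 8 active + 2 placebo. Cohort: 4 active + 1 placebo (section 3.1). Threshold: more than 50% (section 3.3.4.2). The protocol states no count for this criterion, so there is no figure to reproduce beyond the design, 5 × (8 + 2) = 50 subjects.

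**Step 1: counts.** The smallest whole number above half of 10 is 6 (5/10 = 50%, not met). The smallest above half of 8 is 5 (5/8 = 62.5%). With no placebo event, the literal rule needs 6/8 = 75% of active subjects.

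**Step 2: where the readings differ.** All combinations were enumerated. For the first cohort, the denominator is taken as the subjects dosed so far; this is an assumption.

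| Stage | Outcome (active, placebo) | Active-only | Literal |
|---|---|---|---|
| Full group | 5, 0 | 5/8: met | 5/10: not met |
| Full group | 4, 2 | 4/8: not met | 6/10: met |
| First cohort | 2, 1 | 2/4: not met | 3/5: met |

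They agree everywhere else.

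**Step 3: chance of meeting the criterion, one look at the full group.** Let X ~ Bin(8, p) be active events and Y ~ Bin(2, q) placebo events, independent. Active-only: P(X ≥ 5). Literal: P(X + Y ≥ 6). The rates p and q are assumptions.

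Check at p = 0.6, q = 0: P(X ≥ 5) = 27.87 + 20.90 + 8.96 + 1.68 = 59.41%. The literal figure drops the X = 5 term: 59.41 − 27.87 = 31.54%.

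**Step 4: two looks.** Section 3.1 makes the criteria a condition for each dosing, so a first cohort that meets the rule stops things before the full group is reached. Let X₁, X₂ ~ Bin(4, p) and Y₁, Y₂ ~ Bin(1, q) be the two cohorts.

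- Active-only: X₁ ≥ 3, or X₁ + X₂ ≥ 5.
- Literal: X₁ + Y₁ ≥ 3, or X₁ + X₂ + Y₁ + Y₂ ≥ 6.

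Check at p = 0.6, q = 0. First look, both readings: P(X₁ ≥ 3) = 34.56 + 12.96 = 47.52%.

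- Active-only adds P(X₁ = 2)·P(X₂ ≥ 3) + P(X₁ = 1)·P(X₂ = 4) = 0.3456 × 0.4752 + 0.1536 × 0.1296 = 18.41%, total 65.93%.
- Literal adds P(X₁ = 2)·P(X₂ = 4) = 0.3456 × 0.1296 = 4.48%, total 52.00%.

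| Active rate p | One look: active-only vs literal (q = 0–10%) | Loss, points | Two looks: active-only vs literal (q = 0–10%) | Loss, points |
|---|---|---|---|---|
| 60% | 59.4% vs 31.5–37.1% | 22–28 | 65.9% vs 52.0–56.5% | 9.4–13.9 |
| 70% | 80.6% vs 55.2–60.1% | 20–25 | 84.2% vs 71.5–74.9% | 9.3–12.7 |
| 80% | 94.4% vs 79.7–82.5% | 12–15 | 95.6% vs 88.2–89.9% | 5.7–7.3 |

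The first-cohort look roughly halves the loss, because most 5-of-8 patterns already have 3 or 4 events in the first cohort.

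**Step 5: where the effect shrinks or reverses.** With one look and placebo rates of 20–30%, the literal figures rise to 42.5–47.8%, 64.9–69.4% and 85.2–87.6%. With equal rates in both arms there is no dilution (63.3%, 85.0% and 96.7% literal). With two looks and 10% on placebo, the literal rule triggers slightly more often at low active rates: 4.3% vs 3.2% at 20% active, and 11.5% vs 10.9% at 30%.

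**The case against.** **Other protection remains.** One drug-related SAE ends escalation. Sections 2.1 and 2.3 require the preceding dose to have been safe with acceptable tolerability. Section 3.1 requires that no dose-limiting events occurred and a documented Safety Review in which the Principal Investigator and the trial clinical monitor decide jointly. Section 4.1.5.1 lists the clinical monitor among the unblinded sponsor functions, so a split of 5 of 8 against 0 of 2 should be visible to a co-decider. This stands, and it limits the consequence. A reader might infer that missing the criterion lets the trial escalate through 5 of 8 poorly tolerating subjects. The documents do not support that: missing it leaves the decision to judgement and authorises nothing. But for non-serious events those safeguards are discretionary, and they do not correct the threshold.

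**High event rates are unlikely.** The losses shown need 60–80% of healthy men to have qualifying events, while section 2.3 reports that single doses were well tolerated. That is fair; the rates are illustrations, not forecasts. A stopping rule is nevertheless written for the unexpected case.

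**A blinded site can apply an all-subjects count.** It can, and it cannot apply an active-only one unaided. But the QT and potassium rules already need allocation, so the protocol has accepted that dependence.

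**The literal rule is sometimes stricter.** True at (4, 2) and, in the first cohort, at (2, 1). A reader might infer that it is uniformly laxer; it is not.

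**Conclusion.** The point holds on the text and the arithmetic: as written, 5 of 8 actively treated subjects with qualifying events and no placebo event falls exactly on 50% and does not end escalation. The protocol does not say whether this was intended.

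The size is modest. With placebo rates of 0–10% and checks after the first cohort and the full group, the chance of meeting the criterion falls by about 9–14 points at a 60% active rate, 9–13 at 70% and 6–7 at 80%. The one-look losses of 12–28 points apply only if nothing is counted until the full group is dosed, which sits badly with the within-group condition in section 3.1. These are chances of meeting this one criterion, not of escalating. They assume independent subjects, a common rate within each arm, a denominator of subjects dosed so far, and two looks as a simplification of ongoing monitoring.

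At true active rates of 50% or below, a lower chance of triggering means fewer chance stops, not missed intolerability. The change should be made because it is cheap and concerns a safety stop, not because subjects would otherwise be unprotected.

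**What to change.** In section 3.3.4.2, make the AE criterion apply to *more than 50% of the subjects on active drug at one dose level (at least 5 of 8 in a full group)*. Add one sentence saying that the unblinded sponsor clinical monitor keeps this count on an ongoing basis, for the Safety Review and for the within-group dosing check in section 3.1, and tells the site only whether the criterion is met. If an all-subjects count was intended, state 6 of 10 and explain why this rule differs from the QT and potassium rules.

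The cost is one phrase and one sentence, with no new unblinding. The small downside is that the blinded site cannot apply the count alone and a stop could hint at allocation, as is already so for the QT and potassium rules.
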